Trial Coordination. After training, the Sponsor or the trial coordinator will orient the provider to the study protocol and assign every provider a unique Provider Number. The trial coordinator will arrange with the hospital staff to conduct the trial at scheduled times during the study period. Administration of the trial requires two hospital providers who have been trained to use the device, the trial coordinator,

and a patient.

Patient Enrollment. Hospital providers will screen patients who have been admitted to the Labor and Delivery unit for eligibility. Posters advertising the trial will also be displayed on the Labor and Delivery unit. Once identified, hospital providers will ask eligible patients if they are interested in participating. If a patient indicates interest, the trial coordinator will complete an informed consent. The patient will sign the Patient Informed Consent Form.

Randomization. The trial coordinator will assign the participant a Subject Number from one to 50, in sequential order. (The first patient enrolled is assigned #1, the second enrolled is assigned #2, and so on.) The trial coordinator will then randomize the patient to either the Control Group or the Device Group using a randomization matrix generated by a computer randomization program.

Data Collection. The trial coordinator will inform two trained providers that the patient has agreed to participate in the trial. The trial coordinator will accompany one hospital provider to the patient's hospital room. The second provider will wait outside the room, in a place where s/he cannot hear the interaction in the room. The trial coordinator will re-affirm consent with the patient.

If the patient is randomized to the Control Group: The first provider will introduce him/herself and inform the patient that s/he is going to conduct a cervical examination. The trial coordinator will record the time of the first exam. The provider will complete a cervical examination following the standard techniques s/he uses on a regular basis, using sterile gloves. The provider will dispose of the gloves. The first provider will write his/her measurement of cervical dilation on the first Data Collection Form and fold the sheet of paper. Readings may be integers or fractional answers. The coordinator will take the folded sheet of paper and will not read the value. The first provider will then leave the hospital room. S/he will not speak to the second provider.

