The second provider will enter the hospital room. The second provider will introduce him/herself to the patient and explain that s/he is going to perform a cervical examination. The trial coordinator will record the time of the second exam. The second exam must be completed within 10 minutes of the first exam. The second provider will complete a cervical examination following standard techniques. The provider will write his/her measurement of cervical dilation on a second Data Collection Form, fold the form, and hand it to the trial coordinator. Readings may be integers or fractional answers. The second provider will leave the room.

If the patient is in the Device Group: The first provider will introduce him/herself and inform the patient that s/he is going to conduct a cervical examination and confirm that the patient is ready to proceed. The trial coordinator will record the time of the first exam. The first provider will complete a cervical examination with a DilaCheck® device and sterile gloves using the techniques taught during training.

During or after the examination, before looking at the DilaCheck® device or his/her hand, the provider will verbally report his/her subjective cervical dilation measurement to the trial coordinator. Readings may be integers or fractional answers. The trial coordinator will record this number. The first provider will then look at the DilaCheck® device and read the measurement from the DilaCheck® measuring tape.

The trial coordinator will take a photograph from a secure camera of the DilaCheck® measurement. The trial coordinator may choose to take multiple photographs to ensure a clear image is captured. The coordinator and provider will use a neutral background to ensure no private health information (such as an image of the patient participant or hospital room) is included in the photograph. A white sheet of paper with the subject number will be provided to serve as a blank, secure background for the photograph(s).

The first provider will record two readings of the DilaCheck® measurement. The provider will write his/her measurements on the first Data Collection Form, fold the form, and hand it to the trial coordinator. The first will be his or her reading of the exact DilaCheck® measurement, which may be a fraction (any fraction). The second reading will be his or her reading of the DilaCheck® measurement rounded to the nearest integer; i.e. the second response can only be an integer, not a fraction.

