The first provider will dispose of the gloves and device. The first provider will then leave the hospital room. S/he will not speak to the second provider.

The second provider will enter the hospital room. The second provider will introduce him/herself to the patient and explain that s/he is going to perform a cervical examination. The trial coordinator will record the time of the second exam. The second exam must be completed within 10 minutes of the first exam. The second provider will complete a cervical examination as above using a DilaCheck® device. The second provider and trial coordinator will repeat the same steps as described above for the first provider. The second provider will leave the room.

Patient Survey. The trial coordinator will then ask the patient to answer the questions on the Patient Survey. The survey will elicit relevant biological and demographic variables including age, race, ethnicity, gestational age, weight, and use of epidural anesthesia. It will assess the patient's discomfort with the examinations, confidence in the accuracy of the measurements, and satisfaction with the examinations. Patients will be asked to report any side effects they experienced and to provide any comments they have.

Patient Reimbursement. The trial coordinator will offer the patient a \$25 gift certificate to thank her for participating. The patient will sign a receipt to confirm that she received the gift certificate.

Provider Survey. At the end of the trial, the trial coordinator will ask all participating providers to complete the Provider Survey. The survey will elicit the provider's years of experience, role on Labor and Delivery, opinions about inter-examiner agreement using standard methods and using DilaCheck®, and ease of use and satisfaction with the device. The survey will ask whether providers experienced any adverse events and if their patients experienced any adverse events during the trial. They will have the option to provide comments.

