Photograph Review. The Sponsor will train an independent reviewer to read DilaCheck® measurements. The reviewer will be provided the photographs taken of DilaCheck® measurements. The reviewer will report two measurements for each photograph. The first will be his/her reading of the exact DilaCheck® measurement, which may be a fraction. The second reading will be his/her reading of the DilaCheck® measurement rounded to the nearest integer; i.e. the second response can only be an integer, not a fraction.

Continuous Feedback. After any individual provider completes five examinations with DilaCheck®, the provider will be provided feedback about whether his/her DilaCheck® measurement readings match those of the independent reviewer.

Power Calculation. The planned enrollment in the study is 50 patients. The following assumptions were used for the power calculations. The agreement in the Control Group was projected to be 49%,⁴ and the agreement in the Device Group was projected to be 90%, based on the results of the simulator trial. The standard deviation was projected to be 23, also based on the standard deviation in the prior simulator trial. With a two-tailed test with $\alpha=0.05$, a sample size of five yields 80% power. However, a trial with five participants will not yield the desired robustness in evaluation of a novel medical device. Instead, a sample size of 25 subjects in each group is planned to allow for examinations across a wide range of patients and providers. A sample size of 50 yields a power of 100% to detect a difference between the two methods given the above assumptions.

Statistical Analysis. The statistical analysis will use a two-tailed level of significance of 0.05. Using SPSS, the proportion of examinations in each group for which the two providers' examinations differed will be determined. A Students T test will be performed to determine whether this difference is significant. The number of examinations for which providers' answers differed by one centimeter and by two or more centimeters for each group will be determined. A Students T test will be performed to determine if the frequency of variation of one centimeter significantly differed between groups. A Students T test will be performed to determine if the frequency of variation of two or more centimeters significantly differed between groups. These analyses will be completed for both the fractional and integral (non-fractional) sets of DilaCheck® measurement readings.

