For participants in the DilaCheck® arm, the subjective and DilaCheck®

DilaCheck® Trial

measurements will be plotted along an X-Y axis and the Pearson correlation coefficient between the two data sets will be calculated. This analysis will be completed for both the fractional and integral (non-fractional) sets of DilaCheck® measurement readings.

The photographs of the DilaCheck® measurements will be read by an independent, blinded reviewer to report the DilaCheck® measurements. The provider's and reviewer's DilaCheck® measurements will be plotted along an X-Y axis and the Pearson correlation coefficient between the two data sets will be calculated. This analysis will be completed for the fractional and integral (non-fractional) sets of DilaCheck® measurement readings.

The correlation between the providers' subjective and DilaCheck® measurements will be analyzed over time. To do so, for providers who complete at least 10 exams, the correlation of the two measurements in the provider's first half of examinations will be compared to the providers' second half of measurements. A T-test will be completed to determine whether the two correlations differ significantly. The analysis will be repeated for both the fractional and integral (non-fractional) sets of DilaCheck® measurement readings and using the data sets of readings from the independent reviewer.

The average pain score in each group will be calculated, and a Students T test will be performed to determine whether pain scores differed significantly between groups. Using logistic regression whether provider number, patient age, gestational age, weight, or epidural status significantly impacted likelihood of agreement or pain score within each group will be determined. The average provider confidence in accuracy will be calculated, and a Students T test will compare if patients' confidence differs significantly between groups. Logistic regression will be used to determine if provider experience or training significantly predicted likelihood of agreement.

Any additional statistical analysis appropriate for the data collected will be performed. For the qualitative data, including descriptions of adverse events and feedback, each of the responses will be reviewed individually. Any serious adverse events will be reported. Any informative feedback or themes in the feedback will also be collated.

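### Both device exams of a patient are photographed under the same Subject Number, so the blinded reviewer can pair the images, and the label alone does not show whose exam is pictured

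*Combined protocol and SAP*

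**What the plan says.** Under Randomization, the identifier belongs to the patient: "The trial coordinator will assign the participant a Subject Number from one to 50, in sequential order". Under Data Collection (Device Group), that identifier is the only mark described on the photograph background: "A white sheet of paper with the subject number will be provided to serve as a blank, secure background for the photograph(s". An exam may produce more than one image: "The trial coordinator may choose to take multiple photographs to ensure a clear image is captured". For the second exam, due within 10 minutes of the first, "The second provider and trial coordinator will repeat the same steps as described above for the first provider".

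Under Photograph Review, "The reviewer will be provided the photographs taken of DilaCheck® measurements", and two values (exact and integer) are reported for each photograph. Statistical Analysis states: "The photographs of the DilaCheck® measurements will be read by an independent, blinded reviewer". What the reviewer is blinded to is not said.

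The reviewer's values have three planned uses: the Pearson correlation of provider with reviewer readings, the feedback after a provider's fifth device exam on whether his or her "readings match those of the independent reviewer", and a repeat of the first-half versus second-half analysis using the reviewer's readings. The Protocol Summary lists agreement between provider and reviewer readings as a secondary outcome.

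**The concern.** Two separate weaknesses follow from a label set per patient instead of per exam.

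**Linked images.** The reviewer's reading serves as an outside check on how providers read the tape. For that purpose each image should be read on its own. A shared number tells the reviewer that two images belong together. A reviewer who knows or works out that they show two exams a few minutes apart has a reason to expect similar values. The exact (fractional) reading leaves the most room for such an expectation to act.

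**Unlabelled exam.** All three uses need each image tied to the provider whose exam it shows. The Subject Number cannot do this, because two providers examine each device patient. With three images under one number, for example, the label does not show whether they split as two and one or as one and two.

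At stake are a listed secondary outcome, the accuracy of what individual providers are told during the trial, and a supporting analysis. The over-time analysis is limited to providers with at least 10 exams, so a single misassigned point there would weigh more than in the pooled correlation.

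**Working it through.** The plan gives no figure on this point to reproduce. The check is a reading of the text and then a scale for the second weakness.

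**What the label does and does not show**

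| Item | What the text gives | Consequence |
|---|---|---|
| Unit of the label | Patient, 1 to 50 (Randomization) | Same number on both exams |
| Other marks in the image | None described; the sheet is otherwise blank | Provider Number and exam order are not stated to be visible |
| Preparation for review | Photographs are provided; no re-coding, cropping or shuffling described | Pairs are visible to the reviewer |
| Providers' readings | Written on separate folded forms | Not revealed by the label |
| Link outside the image | Exam times recorded; one form per exam; exams in sequence | A link could be kept, but the step is not written down |

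**Number of exams and images**

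Input: 25 patients in the Device Group (Power Calculation), 2 exams each.

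25 × 2 = 50 exams, hence at least 50 photographs, in 25 sets that share a label.

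**When a mix-up changes a result**

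Let p1 and p2 be the two providers' readings for a patient, and r1 and r2 the reviewer's readings of the matching images. Swapping the images changes the pair's contribution to the sum of cross-products in the pooled correlation by

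(p1·r1 + p2·r2) − (p1·r2 + p2·r1) = (p1 − p2)(r1 − r2).

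This is zero if either pair of readings is equal. The means and variances do not change. For feedback to one provider, and for the over-time analysis with reviewer readings, a swap matters only if r1 and r2 differ. One swapped pair misplaces 2 of 50 points (2/50 = 4%), but it alters the data only under these conditions.

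**How many pairs could be affected**

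Pairs that differ = 25 × (1 − agreement). The 90% is the plan's projection for the Device Group. The 75% is an assumption. The 49% is the plan's control-arm projection, used here as a low bound. The last column assumes that images are assigned to exams by coin toss, which is an extreme case and not something the plan implies.

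| Agreement | Pairs that differ | Of these swapped, if coin toss |
|---|---|---|
| 90% | 25 × 0.10 = 2.5 | 1.25 |
| 75% | 25 × 0.25 = 6.25 | 3.125 |
| 49% | 25 × 0.51 = 12.75 | 6.375 |

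The plan does not say whether the 90% refers to integer or fractional readings. Fractional readings could differ more often.

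**Anchoring**

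No calculation is possible. The documents give nothing on how far a reading of one image would pull the reading of its partner.

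**The case against.** The strongest case on the other side is as follows.

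- **The sheet is a privacy measure.** It is described as a plain background that keeps patient information out of the picture, not as the index of the photographs. That it is the only mark is inferred from silence. This stands, and it is why the second weakness is mostly missing detail.
- **The workflow keeps the exams apart.** One coordinator photographs the first exam and takes the first form, and the first provider leaves before the second enters. Exam times are recorded. A reader might infer that the photographs cannot be traced to providers. The documents do not support that: the coordinator could keep the link, although no step says so.
- **Blinding is not shown to fail.** A reader might infer that the shared number breaks the reviewer's blinding. In a comparison of provider with reviewer, the natural meaning is blinding to the providers' readings, and the number reveals none of them. What remains is that the reviewer can pair images.
- **Anchoring is only a possibility.** The reviewer reads a marked tape, and the text does not say the reviewer is told of the two-exam design. No agreement between exams based on reviewer readings is planned, which is where anchoring would do most harm. This limits the weight of the point but does not remove it, since the pairing is visible and can be avoided.
- **Shuffling all images at once would conflict with Continuous Feedback**, which needs reviewer readings while the trial runs. This is correct, and the fix has to allow for it.

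**Conclusion.** The point holds as a minor one. As written, the reviewer can tell which images come from the same patient, and the label does not by itself identify the exam. Changing the stated label would remove a route for one reading to influence another in a listed secondary outcome.

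The limits matter. The primary outcome rests on the providers' own readings and is not affected. A reader might infer from the 25 shared labels that all 50 device exams are compromised. That figure counts labels, not errors, and the documents give no rate for mix-ups. At the projected 90% agreement, a swap could change results in about 2.5 of 25 pairs. The size of any anchoring is unknown.

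The conclusion assumes that no other mark appears in the image and that photographs reach the reviewer as taken. Both are inferred from what the plan describes, and neither is stated outright.

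**What to change.** - Replace the Subject Number on the background sheet with a unique random code for each exam. Several images of one exam share that code.
- Have the coordinator hold a key linking the code to Subject Number, exam order and Provider Number.
- Present images to the reviewer in random order within each review batch, so that feedback after five exams can still run.
- State in Photograph Review what the reviewer is blinded to, and which image counts when several are taken.

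The cost is about 50 coded sheets (25 × 2), a key and a simple shuffle for each batch. Sample size, patient procedures and the primary analysis do not change. The downside is that the image no longer carries the Subject Number, so an error in the key would lose both the patient and the provider link. Writing the code on the Data Collection Form at the time of the exam would give a second record.

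Adding only an exam number beside the Subject Number would settle which exam is pictured, but it would leave the pairing visible to the reviewer.

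### Device whole-centimetre readings are rounded by hand with no rule for halves, so two identical half-centimetre readings can be scored as a disagreement in the integer analysis

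*Combined protocol and SAP*

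**What the plan says.** Under Data Collection, the first provider in the Device Group writes two numbers from the tape. The first is the exact reading, for which any fraction is allowed. For the other: "The second reading will be his or her reading of the DilaCheck® measurement rounded to the nearest integer", with the restriction that "the second response can only be an integer, not a fraction". The second provider does likewise: "The second provider and trial coordinator will repeat the same steps as described above for the first provider".

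Photograph Review gives the independent reviewer the same task: "The second reading will be his/her reading of the DilaCheck® measurement rounded to the nearest integer".

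Under Statistical Analysis, the main comparison is stated as follows: "the proportion of examinations in each group for which the two providers' examinations differed will be determined". Counts of pairs that differ by one centimetre and by two or more come next. Then: "These analyses will be completed for both the fractional and integral (non-fractional) sets of DilaCheck® measurement readings". The protocol does not name either set as primary.

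No section says how a value ending in .5 is to be rounded, and none says that the integer is computed from the recorded exact value. Control Group providers write one reading and are not made to round ("Readings may be integers or fractional answers"), so the gap lies within the device arm.

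**The concern.** The endpoint is whether two written numbers are the same, so any step that can turn equal readings into unequal numbers acts directly on it. The nearest integer to 4.5 is not defined. If both examiners read 4.5 and one writes 4 while the other writes 5, the fractional run scores agreement and the integer run scores a one-centimetre difference. That difference reflects rounding habit, not the device.

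At stake is the integer version of the agreement comparison and of the one-centimetre count. Since neither set is designated primary, the affected set could carry the main result. The reviewer's integers, which feed the provider-versus-reviewer correlation, have the same gap.

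**Working it through.** **The plan's own figures.** Power Calculation uses 49% and 90% agreement, SD 23, two-sided alpha 0.05. By the normal approximation for two means, n = 2 × (1.960 + 0.842)² × 23² / 41² = 4.9, so 5 per group, with 80.5% power. At 25 per group, 41 / (23 × √(2/25)) = 6.30, and power is 99.999%. Both stated figures reproduce, and neither depends on the rounding rule.

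**Chance of a spurious disagreement.** Let each examiner independently round a half up with probability q. Two identical x.5 readings get different integers with probability 2q(1-q):
- q = 0.5: 50%
- q = 0.75: 37.5%
- q = 0.8 (or 0.2): 32%
- one fixed rule: 0

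**Effect on integer agreement.** Let h be the share of device pairs with identical x.5 readings. The loss is h × 2q(1-q). Pairs with unequal readings add no net loss if dilation is spread evenly: rounding a half down removes a match with the integer above and creates one with the integer below.

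The documents do not give h. Starting from the projected 90%, with q = 0.5:
- h = 5%: 87.5% agreement, 0.6 of 25 pairs lost
- h = 10%: 85%, 1.25 pairs
- h = 20%: 80%, 2.5 pairs
- h = 30%: 75%, 3.75 pairs

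**Linking h to recording precision.** Assume that true dilation is uniform and that each tape reading has independent error with SD 0.1 cm. The mean absolute difference between two readings is 2 × 0.1 / √π = 0.113 cm. This is also the chance that a whole-centimetre rounding boundary falls between them, so rounding straight from the tape gives 1 - 0.113 = 88.7% agreement. Deriving the integer from a coarser written value by one fixed rule gives the same 88.7%, because the boundaries move but stay 1 cm apart.

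If ties are instead broken at the examiner's discretion from the written value, h is the exact-match (fractional) agreement times the share of values ending in .5. The fractional agreement comes from a simulation of 2 million pairs under these assumptions. Power is for the planned t test on 0/1 outcomes, 25 per arm, against 49%.

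| Exact value written to | Fractional agreement | Share ending in .5 | h | Loss, q = 0.75 / 0.5 (points) | Integer agreement | Power |
|---|---|---|---|---|---|---|
| 0.1 cm | 27% | 1/10 | 2.7% | 1.0 / 1.4 | 88% / 87% | 0.88 / 0.87 |
| 0.25 cm | 57% | 1/4 | 14.2% | 5.3 / 7.1 | 83% / 82% | 0.77 / 0.71 |
| 0.5 cm | 77% | 1/2 | 38.5% | 14.4 / 19.2 | 74% / 69% | 0.48 / 0.34 |

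Without tie noise, integer agreement is 88.7% and power is about 0.90. Direct simulation of the hand-rounded integers gives the same agreement to the nearest percent.

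**The case against.** The strongest reply is that the instruction is to round the measurement on the tape, not the number just written. An examiner who writes a coarse 4.5 may still see on which side of the midpoint the tape falls. If so, nothing is lost. A reader might infer that the integer is fully determined by the exact value on the form and that the manual step therefore adds only error. The documents do not support that: it holds only if the first reading is written at the tape's full resolution, and the protocol gives no graduation. This part of the reply stands.

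The large losses need two things together: recording to 0.5 cm, although the form asks for the exact value, and ties broken from that written number. Nothing in the documents says examiners will do either.

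Safeguards exist. Provider Training follows a script with a competency test, and Continuous Feedback compares a provider's readings with the reviewer's after five device examinations. The script is not in the documents and may contain a rounding convention. The protocol and its analysis section state none, so this narrows the gap without closing it.

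The remedy can also be questioned. With 0.5 cm recording and halves rounded up, 25% of derived integers differ from the tape's own nearest integer, and the mean shift is 0.25 cm upward. This is a real cost for the integer values themselves. It does not harm the agreement endpoint, since both examiners are shifted alike and simulated agreement stays at 88.7%.

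**Conclusion.** The gap is real but limited. Hand rounding with no rule for halves lets two identical x.5 readings be scored as one centimetre apart in the integer run. The fractional run is unaffected.

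The size rests on assumed precision, rounding habits and a reading SD of 0.1 cm. It runs from no loss (rounding from the tape, about 89% agreement), through 87-88% and 82-83% (0.1 and 0.25 cm recording), to 69-74% in the worst case of 0.5 cm recording.

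A reader might infer that the trial stands to lose half its power or more. The figures of 0.48 and 0.34 belong to that worst case and to the integer run alone. At 0.1 cm recording, power stays at about 0.87 or higher.

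A reader might also infer a bias towards the device, because providers state a subjective estimate before looking at the tape and could break a tie towards it. That is possible, but the documents give nothing from which to size it. Pure tie noise lowers device agreement and so works against the device.

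**What to change.** Three short changes:

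1. In Data Collection and Photograph Review, ask for the exact reading at the tape's finest graduation.
2. In Statistical Analysis, state that the integer set for the agreement analyses is derived by program from the exact readings of providers and reviewer, with one tie rule fixed before analysis (for example, halves up).
3. Keep the hand-rounded integers as a sensitivity analysis, and report how often they differ from the derived ones.

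The exact readings are already on the forms, so no new data are needed; the cost is a few sentences and a line of code. There are two small downsides. If exact readings are still written coarsely, derived integers can be shifted from the tape's nearest integer. Examiner rounding variability, which is arguably part of using the device, will then appear only in the sensitivity analysis.
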